| | 
 • Serum albumin ≥ 25 g/L; • Serum total bilirubin $\leq 1 \times$ upper limit of normal (ULN); • Alanine aminotransferase (ALT), aspartate aminotransferase (AST) and alkaline phosphatase (AKP) $\leq 2.5 \times$ULN; • Serum creatinine (Cr) $\leq 1.5 \times$ULN or Cr clearance > 50 mL/min (Cockcroft-Gault formula as below) Man: Cr clearance = $((140 - \text{age}) \times \text{weight}) / (72 \times \text{serum Cr})$ Woman: Cr clearance = $((140 - \text{age}) \times \text{weight}) / (72 \times \text{serum Cr}) \times 0.85$ Weight unit: kg; serum Cr unit: mg/mL; 
11. Women of childbearing potential: must agree on abstinence (avoid heterosexual intercourse) or use of contraception methods with annual contraceptive failure rate of $< 1\%$ following the signature of informed consent form until at least 120 days after the last dose of study drug. The serum human chorionic gonadotropin (HCG) test must be negative within 7 days prior to enrollment in the study; and the subjects must not be in lactating period.
 
If the female subject has menses, has not reached postmenopausal state (absence of menses for \geq consecutive 12 months, with no other reason found except menopause) and has not received sterilization operation (e.g., hysterectomy, bilateral tubal ligation or bilateral ovariectomy), she would be considered to have childbearing potential.
 |
| 
Exclusion Criteria
 | 
Subjects who meet any one of the following criteria must not be enrolled in this study:
 
 1. Other active malignant tumor except advanced osteosarcoma within 5 years or simultaneously. Cured localized tumor, for example, basal cell carcinoma of skin, squamous cell carcinoma of skin, superficial bladder cancer, carcinoma in situ of prostate, carcinoma in situs of cervix, breast cancer in situ may be enrolled; 2. History of gastrointestinal hemorrhage within 6 months prior to the start of study treatment or clear tendency of gastrointestinal hemorrhage, for example, esophageal and fundal varices with hemorrhagic risk, locally active peptic ulcer, persistent fecal occult blood (+) (the fecal occult blood test can be repeated if it is positive at baseline, and gastroduodenoscopy |

| | |
|--|--|

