| | 
[EGD] would be needed if it is still positive in repeated test; the patient can not be enrolled if the EGD shows esophageal and fundal varices with hemorrhagic risk);
 
 3. Abdominal fistula, gastrointestinal perforation or intraperitoneal abscess within 6 months prior to the start of study treatment; 4. Known genetic or acquired hemorrhage (e.g., coagulation dysfunction) or thrombotic tendency, for example, patient with hemophilia; current or recent (within 10 days prior to the start of study treatment) use of full-dose of oral or intravenous anticoagulant or thrombolytic drug for the purpose of treatment (preventive use of low-dose aspirin or low molecular weight heparin is allowed); 5. Current or recent (within 10 days prior to the start of study treatment) use of aspirin (> 325 mg/day) or dipyridamole, ticlopidine, clopidogrel and cilostazol; 6. Thrombosis or thromboembolic event within 6 months prior to the start of study treatment, for example, cerebrovascular accident (including transient ischemic attack, cerebral hemorrhage, cerebral infarction), pulmonary embolism; 7. Cardiac clinical symptom or disease that is not well controlled, for example, (1) > Grade II cardiac insufficiency in accordance with New York Heart Association (NYHA) criteria or color Doppler echocardiography: LVEF (left ventricular ejection fraction) <50%; (2) unstable angina pectoris; (3) myocardial infarction within one year prior to the start of study treatment; (4) clinically significant supraventricular or ventricular arrhythmia requiring treatment or intervention; (5) QTc > 450 ms (males) or QTc > 470ms (females) (QTc interval is calculated by Fridericia formula; In case QTc is abnormal, it can be detected for three times at an interval of 2 minutes and the average will be taken); 8. Hypertension that can not be well controlled through antihypertensive drugs (systolic blood pressure \geq140 mmHg or diastolic blood pressure \geq90 mmHg) (based on the average of BP readings acquired from \geq2 measurements), allowing to reach the above parameters by the use of antihypertensive therapy; previous hypertensive crisis or hypertensive encephalopathy; 9. Major vascular disease within 6 months prior to the start of study treatment (for example, aortic aneurysm |
|--|--|

- requiring surgical repair or peripheral arterial thrombosis in recent days);
10. Serious, uncured or splitting wound and active ulcer or untreated bone fracture;

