 11. Major surgical therapy within 4 weeks prior to the start of study treatment (except diagnosis), or expected major surgery during the study;
 12. Inability or unwilling to swallow tablets, malabsorption syndrome or any condition affecting gastrointestinal absorption;
 13. Intestinal obstruction and/or clinical signs or symptoms of gastrointestinal obstruction within 6 months prior to the start of study treatment, including incomplete obstruction that is related with the original disease or needs routine parenteral hydration, parenteral nutrition or tube feeding;
 - If the subject has signs/symptoms of incomplete obstruction/ obstructive syndrome/intestinal obstruction at the initial diagnosis receives clear (surgical) therapy to resolve symptoms, the subject may be enrolled;
 14. Evidence on intraperitoneal pneumatosis that can not be explained by puncture or recent surgery;
 15. Previous or current presence of metastasis to central nervous system;
 16. Previous or present history of pulmonary fibrosis, organising pneumonia (e.g., obliterative bronchiolitis), interstitial pneumonia, pneumoconiosis, drug related pneumonitis, idiopathic pneumonia, or allowable previous radiation pneumonitis in the radiation area (fibrosis) for subjects with evidence on active pneumonia or serious pulmonary function impairment on thoracic computed tomography (CT) in screening period that may interfere with the detection and treatment of suspected drug related pulmonary toxicity; active tuberculosis;
 17. Any active autoimmune disease or history of autoimmune disease and expected recurrence (including but not limited to autoimmune hepatitis, interstitial pneumonia, uveitis, enteritis, hypophysitis, vasculitis, nephritis, hyperthyroidism, hypothyroidism [subjects that can be controlled with hormone replacement therapy only can be enrolled]); subjects with skin diseases that does no need systemic treatment, for example, leukoderma, psoriasis, alopecia, those with controlled type I diabetes by insulin or those with asthma that has been completely

- resolved in childhood and with no need of any intervention can be enrolled; while subjects with asthma who need bronchodilator for medical intervention can not be enrolled;
18. Current use of immunosuppressive medication, or systemic corticosteroid therapy to achieve the objective of immunosuppression (Prednisone at the dose of >10mg/day or equivalent), and continuous use within two weeks prior signing informed consent form;

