 19. Use of strong CYP3A4/CYP2C19 inducers, including rifampicin (and its analogues) and St. John's Wort, or strong CYP3A4/CYP2C19 inhibitors within two weeks prior to the signature of informed consent form;
 20. Known history of serious allergy to any monoclonal antibody or targeted anti-angiogenic drug;
 21. Severe infection within 4 weeks prior to the start of study treatment, including but not limited to hospitalization for infection, bacteremia or complications of severe pneumonia; oral or intravenous therapeutic antibiotics within two weeks prior to the start of study treatment (for example, subjects who are given with preventive antibiotics for prevention of urinary tract infection or exacerbation of chronic obstructive pulmonary disease are eligible for participation in the study);
 22. Congenital or acquired immunodeficiency (e.g., HIV infection);
 23. Combined hepatitis B and hepatitis C co-infection;
 24. Previous treatment with other PD-1 antibody or other immunotherapy against PD-1/PD-L1, or previous use of other small molecules of anti-angiogenesis TKI drugs, such as pazopanib, sorafenib;
 25. Palliative radiotherapy for non-target lesions to control symptoms is allowed, but it must be completed at least 2 weeks prior to the start of study treatment, and the adverse event induced by radiotherapy must have resolved/improved to \leq CTCAE Grade 1;
 26. Treatment of other investigational product(s) within 28 days prior to the start of study treatment;
 27. Other factors that may affect the study results or lead to forced termination of the study early as judged by investigators, such as alcoholism, drug abuse, other serious diseases (including mental disorders) requiring concomitant therapy, with serious laboratory

| | |
|--|--|
| | examination abnormality, with family or social factors, that may affect subject's safety. |

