4.2. Exclusion Criteria

Subjects who meet any one of the following criteria must not be enrolled in this study:

1. Other active malignant tumor except advanced osteosarcoma within 5 years or simultaneously. Cured localized tumor, for example, basal cell carcinoma of skin, squamous cell carcinoma of skin, superficial bladder cancer, carcinoma in situ of prostate, carcinoma in situ of cervix, breast cancer in situ may be enrolled;
2. Abdominal fistula, gastrointestinal perforation or intraperitoneal abscess within 6 months prior to the start of study treatment;
3. Known genetic or acquired hemorrhage (e.g., coagulation dysfunction) or thrombotic tendency, for example, patient with hemophilia; current or recent (within 10 days prior to the start of study treatment) use of full-dose of oral or intravenous anticoagulant or thrombolytic drug for the purpose of treatment (preventive use of low-dose aspirin or low molecular weight heparin is allowed);
4. Current or recent (within 10 days prior to the start of study treatment) use of aspirin (> 325 mg/day) or dipyridamole, ticlopidine, clopidogrel and cilostazol;
5. Thrombosis or thromboembolic event within 6 months prior to the start of study treatment, for example, cerebrovascular accident (including transient ischemic attack, cerebral hemorrhage, cerebral infarction), pulmonary embolism;
6. Cardiac clinical symptom or disease that is not well controlled, for example, (1) > Grade II cardiac insufficiency in accordance with New York Heart Association (NYHA) criteria (see APPENDIX 3) or color Doppler echocardiography: LVEF (left ventricular ejection fraction) < 50%; (2) unstable angina pectoris; (3) myocardial infarction within one year prior to the start of study treatment; (4) clinically significant supraventricular or ventricular arrhythmia requiring treatment or intervention; (5) QTc > 450ms (man) or QTc > 470ms (woman) (QTc interval is calculated by Fridericia formula; In case QTc

is abnormal, it can be detected for three times at an interval of 2 minutes and the average will be taken);

7. Hypertension that can not be well controlled through antihypertensive drugs (systolic blood pressure ≥ 140 mmHg or diastolic blood pressure ≥ 90 mmHg) (based on the average of BP readings acquired from ≥ 2 measurements), allowing to reach the above parameters by the use of antihypertensive therapy; previous hypertensive crisis or hypertensive encephalopathy;

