8. Major vascular disease within 6 months prior to the start of study treatment (for example, aortic aneurysm requiring surgical repair or peripheral arterial thrombosis in recent days);
9. Serious, uncured or splitting wound and active ulcer or untreated bone fracture;
10. Major surgical therapy within 4 weeks prior to the start of study treatment (except diagnosis), or expected major surgery during the study;
11. Inability or unwilling to swallow tablets, malabsorption syndrome or any condition affecting gastrointestinal absorption;
12. Intestinal obstruction and/or clinical signs or symptoms of gastrointestinal obstruction within 6 months prior to the start of study treatment, including incomplete obstruction that is related with the original disease or needs routine parenteral hydration, parenteral nutrition or tube feeding;
 - If the subject has signs/symptoms of incomplete obstruction/ obstructive syndrome/intestinal obstruction at the initial diagnosis receives clear (surgical) therapy to resolve symptoms, the subject may be enrolled;
13. Evidence on intraperitoneal pneumatosis that can not be explained by puncture or recent surgery;
14. Previous or current presence of metastasis to central nervous system;
15. Previous or present history of pulmonary fibrosis, organising pneumonia (e.g., obliterative bronchiolitis), interstitial pneumonia, pneumoconiosis, drug related pneumonitis, idiopathic pneumonia, or allowable previous radiation pneumonitis in the radiation area (fibrosis) for subjects with evidence on active pneumonia or serious pulmonary function impairment on thoracic computed tomography (CT) in screening period that may interfere with the detection and treatment of suspected drug related pulmonary toxicity; active tuberculosis;
16. Any active autoimmune disease or history of autoimmune disease and expected recurrence (including but not limited to autoimmune hepatitis, interstitial pneumonia, uveitis, enteritis, hypophysitis, vasculitis, nephritis, hyperthyroidism, hypothyroidism [subjects that can be controlled with hormone replacement therapy only can be enrolled]); subjects with skin diseases that does no need systemic treatment, for example, leukoderma, psoriasis, alopecia, those with controlled type I diabetes by insulin or those with asthma that has been completely resolved in childhood and with no need of any intervention can be enrolled; while subjects with asthma who need bronchodilator for medical intervention can not be enrolled;

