17. Current use of immunosuppressive medication, or systemic corticosteroid therapy to achieve the objective of immunosuppression (Prednisone at the dose

- of >10mg/day or equivalent), and continuous use within two weeks prior to enrollment;
18. Use of strong CYP3A4/CYP2C19 inducers, including rifampicin (and its analogues) and St. John's Wort, or strong CYP3A4/CYP2C19 inhibitors within two weeks prior to signing informed consent form;
 19. Known history of serious allergy to any monoclonal antibody or targeted anti-angiogenic drug;
 20. Severe infection within 4 weeks prior to the start of study treatment, including but not limited to hospitalization for infection, bacteremia or complications of severe pneumonia; oral or intravenous therapeutic antibiotics within two weeks prior to the start of study treatment (for example, subjects who are given with preventive antibiotics for prevention of urinary tract infection or exacerbation of chronic obstructive pulmonary disease are eligible for participation in the study);
 21. Congenital or acquired immunodeficiency (e.g., HIV infection);
 22. Combined hepatitis B and hepatitis C co-infection;
 23. Previous treatment with other PD-1 antibody or other immunotherapy against PD-1/PD-L1, or previous use of apatinib or sorafenib;
 24. Palliative radiotherapy for non-target lesions to control symptoms is allowed, but it must be completed at least 2 weeks prior to the start of study treatment, and the adverse event induced by radiotherapy must have resolved/improved to \leq CTCAE Grade 1;
 25. Attenuated live vaccine therapy administered within 28 days prior to the start of study treatment, or needed administration of such vaccines during SHR-1210 treatment or within 60 days after the last dose of SHR-1210;
 26. Treatment of other investigational product(s) within 28 days prior to the start of study treatment;
 27. Other factors that may affect the study results or lead to forced termination of the study early as judged by investigators, such as alcoholism, drug abuse, other serious diseases (including mental disorders) requiring concomitant therapy, with serious laboratory examination abnormality, with family or social factors, that may affect subject's safety.

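### Section 4.2 omits the GI-haemorrhage exclusion that the synopsis carries as item 2, and the two exclusion lists also differ on prior TKI and the steroid window

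*Protocol*

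**What the plan says.** **Synopsis, Exclusion Criteria, item 2** excludes "History of gastrointestinal hemorrhage within 6 months prior to the start of study treatment" or a clear tendency to GI bleeding. Its examples are varices at risk of bleeding, locally active peptic ulcer and persistently positive fecal occult blood. A positive baseline occult blood test may be repeated. If it is still positive, endoscopy is needed, and "the patient can not be enrolled if the EGD shows esophageal and fundal varices with hemorrhagic risk".

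**Section 4.2** goes from other malignancy (item 1) directly to "Abdominal fistula, gastrointestinal perforation or intraperitoneal abscess within 6 months prior to the start of study treatment" (item 2), which is item 3 of the synopsis. None of its 27 items mentions GI haemorrhage, varices or fecal occult blood.

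The lists differ in three further places:

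- **Prior TKI.** Synopsis item 24 excludes "previous use of other small molecules of anti-angiogenesis TKI drugs, such as pazopanib, sorafenib". Section 4.2 item 23 reads "or previous use of apatinib or sorafenib".
- **Steroids and immunosuppressants.** Synopsis item 18 specifies "continuous use within two weeks prior signing informed consent form". Section 4.2 item 17 specifies "continuous use within two weeks prior to enrollment".
- **Live vaccine.** Section 4.2 item 25 excludes it. The synopsis list has no such item, although Section 5.3.1.2 prohibits live vaccination from 4 weeks before the first dose.

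Both lists open by stating that meeting any single criterion bars enrolment.

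**The concern.** Eligibility has to give one answer for each patient. Here the answer depends on which list the investigator opens, and nothing settles the matter. The only precedence rule, at the start of Section 10, concerns the SAP against the protocol. Section 6.1 admits subjects who meet none of the exclusion criteria without saying which list it means.

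The missing criterion matters for this drug. Section 1.3.1 counts bleeding among the apatinib events that are uncommon but may be fatal. That experience comes mainly from 850 mg daily, and this trial gives 500 mg. Section 5.1.6.2.5 treats persistently positive occult blood on study as GI haemorrhage needing active treatment, yet the same finding at screening has no decision rule in Section 4.2. The later safeguards, namely the occult blood tests in Sections 6.2.2 and 6.2.3 and the haemorrhage stopping rule under Table 5, apply only after dosing has begun.

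There is also a cost in conduct. Section 4.4.1 makes ineligibility found after enrolment, once the sponsor confirms it, a reason to stop treatment. With two lists, whether a treated patient was eligible can be disputed.

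**Working it through.** No formula applies; the check is an item-by-item match of the two lists.

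**1. Count and match.** Each list runs from 1 to 27 without a gap, so the missing item is not a numbered line lost from the text.

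| Synopsis items | Section 4.2 items | Pairs |
|---|---|---|
| 1 | 1 | 1 |
| 3 to 25 | 2 to 24 (each shifted by one) | 23 |
| 26, 27 | 26, 27 | 2 |
| 2 (GI haemorrhage) | none | – |
| none | 25 (live vaccine) | – |

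Shared topics: 1 + 23 + 2 = 26. Each list reaches 26 + 1 = 27 because each has one item that the other lacks. The equal totals hide the omission.

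**2. Compare content within the 26 pairs.** Two pairs conflict in substance: synopsis 24 with Section 4.2 item 23 (prior TKI), and synopsis 18 with Section 4.2 item 17 (steroid window). That leaves 26 − 2 = 24 in agreement.

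**3. Ask whether another Section 4.2 item replaces the missing one.**

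- Item 3 covers inherited or acquired bleeding or thrombotic tendency and full-dose anticoagulants. The synopsis has the same text as item 4, alongside item 2, so the two were written as separate criteria.
- Item 9 reads "Serious, uncured or splitting wound and active ulcer or untreated bone fracture". It arguably reaches an active peptic ulcer, but not a past bleed, varices or occult blood. The synopsis has it separately as item 10.
- Item 27 is investigator judgement. It permits exclusion without specifying it for any of these conditions.
- The inclusion criteria in Section 4.1 contain nothing on GI bleeding.

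**4. Test cases.**

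| Patient | Synopsis | Section 4.2 |
|---|---|---|
| GI bleed 3 months before treatment | Excluded (item 2) | No specific item; item 27 or a broad reading of item 3 only |
| Varices at risk of bleeding | Excluded (item 2) | No specific item |
| Occult blood positive on repeat | Endoscopy; refused outright if it shows risky varices | No rule, though Section 6.1 requires the test |
| Prior pazopanib | Excluded (item 24) | Not excluded by item 23 |
| Prior apatinib | Not named; item 24 speaks of other TKIs | Excluded (item 23) |
| Live vaccine 3 weeks before treatment | Not in list; Section 5.3.1.2 prohibits it | Excluded (item 25) |

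The lists therefore differ in both directions, and neither is simply a shortened form of the other.

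**The case against.** The strongest reply is that, on GI haemorrhage, one list is silent and does not permit what the other forbids. Exclusions can be applied cumulatively, and a careful investigator who honours both lists would refuse a patient with a recent bleed. The trial has one centre, so practice cannot diverge between sites. Items 3, 9 and 27 catch some of these patients.

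It is fair to call the GI point an omission, and applying both lists would avoid the harm. But the protocol does not tell anyone to apply both, and Section 4 presents its own criteria as the conditions for participation. For prior TKI and the steroid window, the texts do state different rules on the same topic.

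Three smaller objections have some force:

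- Synopsis item 2 is not clear on occult blood. It lists persistent positivity as an example of bleeding tendency, yet states refusal after endoscopy only for risky varices. A repeat-positive patient with a clean endoscopy is arguably enrollable under the synopsis too.
- The repair could in principle go the other way, by deleting the item from the synopsis. The occult blood tests in Sections 6.1, 6.2.2 and 6.2.3 and the bleeding warning in Section 1.3.1 favour keeping it.
- The steroid anchor is minor, since the schedule footnotes place consent within two weeks before medication.

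**Conclusion.** The concern holds. Section 4.2 lacks an exclusion that the synopsis states, and no other item supplies it. The lists also conflict on two of their 26 shared topics, and each has one item that the other lacks.

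The consequence is a safety gap at enrolment and an ambiguous eligible population. The number of patients affected cannot be derived from the protocol, and the GI omission leaves sample size, alpha and power unchanged. The TKI conflict bears on who is compared with the 37% null, which Section 10.1 takes from a single-agent apatinib trial, but the protocol gives no basis for estimating any effect on 6-month PFS.

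The conclusion assumes that an investigator may use Section 4.2 as the working list. Of the discrepancies, the GI item carries the most weight and the steroid anchor the least.

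**What to change.** Put one identical exclusion list in the synopsis and in Section 4.2:

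1. Insert synopsis item 2 in full into Section 4.2, including the repeat occult-blood and endoscopy rule, so that the screening result has a decision rule. While doing so, state whether a repeat-positive test excludes on its own or only when endoscopy shows varices at risk of bleeding.
2. Add the live-vaccine exclusion (Section 4.2 item 25) to the synopsis.
3. Use one prior-TKI exclusion in both: any earlier small-molecule anti-angiogenic TKI, including apatinib, sorafenib and pazopanib. This joins the two existing texts; if the sponsor intends a narrower rule, both lists should state that one.
4. Count the two-week steroid window from enrolment in both. Either anchor would serve if used consistently.

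The cost is protocol wording. Section 6.1 already requires the occult blood test at screening. The Schedule of Activities does not list that test, and the screening procedures do not mention endoscopy for a repeat positive, so a line in each place would complete the change.
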